10.4.2	Historical Data.....	7
10.4.3	Missing Data.....	8
10.5	DATA MANAGEMENT	8
11	STUDY MANAGEMENT	8
11.1	STUDY MONITORING PLAN	8
11.2	CENTRAL LABORATORY COMPLIANCE.....	8
11.3	PATIENT ADHERENCE WITH STUDY MEDICATION	8
11.4	DEVIATIONS FROM THE PROTOCOL.....	9
11.5	ADHERENCE TO THE PROTOCOL.....	9
11.6	AMENDMENTS TO THE PROTOCOL	9
11.7	OBLIGATIONS OF INVESTIGATORS.....	9
12	STUDY FINANCES	9
12.1	FUNDING SOURCE	9
12.2	CONFLICT OF INTEREST	9
12.3	SUBJECT STIPENDS OR PAYMENTS.....	9
13	REFERENCES	9

Protocol Revision History

The following describes the revision history for this protocol.

Protocol Version	History of Changes
Protocol Version 1	Initial version approved by the IRB
Protocol Version 2	
The following amendments to this protocol were made:
 
• Tacrolimus dosing: To meet the current standard of care at UNC, the initial dosing of tacrolimus was changed from 0.3 to 0.2 mg/kg/day for CYP3A5 expresser and from 0.15 mg/kg/day to 0.1 mg/kg/day for CYP3A5 nonexpresser; tacrolimus is to be given in two divided doses with a maximum total daily dose of 20 mg/day. Safety data regarding the initial tacrolimus dosing of 0.1 mg/kg/day and 0.2 mg/kg/day are available in the drug's package insert.• Safety monitoring: The statement "AEs will be collected following kidney transplantation" was added in Section 9.2 to clarify that AEs will be collected after subjects have received kidney transplantation and are eligible to receive tacrolimus.
Protocol Version 3	A sentence in the table of schedule of activities was added to clarify that assessment of drug-related AEs may be done in person or by phone.

List of Abbreviations

The following abbreviations and specialized terms are used in this study protocol.

Abbreviation or specialized term	Explanation
AE	Adverse event
ADR	Adverse drug reaction
C ₀	Trough concentration
CFR	Code of Federal Regulations
CGI	Cancer Genetics Incorporated
CI	Confidence Intervals
CL	Central Laboratory
CLIA	Clinical Laboratory Improvement Amendment
CrCl	Creatinine Clearance
eGFR	Estimated Glomerular Filtration Rate
CPIT	Center for Pharmacogenomics and Individualized Therapy
CRF	Case Report Form
FDA	Food and Drug Administration
GCP	Good Clinical Practice
GLP	Good Laboratory Practice
HIPAA	Health Insurance Portability and Accountability Act
ICH	International Conference on Harmonization
IEC	Independent Ethics Committee
IRB	Institutional Review Board
ITT	Intent-to-treat
PD	Pharmacodynamics
PHI	Protected health information
PID	Participant identification number
PK	Pharmacokinetic
REDCap	Research Electronic Data Capture
SAE	Serious adverse event
SOP	Standard operating procedure
SNP	Single nucleotide polymorphism
UNC-CH	University of North Carolina in Chapel Hill

1 Study Summary

Title	Study of Pharmacogenomic-guided Tacrolimus Dosing and Monitoring in Kidney Transplant Recipients
Short Title	Pharmacogenomic-guided Dosing of Tacrolimus
Protocol Number	16-2073
Phase	Postmarketing; Phase 4
Methodology	
This is a study of pharmacogenomic-guided tacrolimus dosing and drug monitoring in kidney transplant recipients. The pharmacogenomic group will partake in a 12-month study comprising of two periods, Genotype-Guided Initial Dosing Intervention and Follow-up.
 
Briefly, patients currently on the waitlist to receive kidney transplantation at UNC-CH who are being seen by the multi-disciplinary kidney transplantation team will be screened for eligibility. At the pre-intervention assessment (Study Day 0), buccal swab samples for genotyping will be collected on all eligible patients who provided informed consent (performed in real time). All buccal swab samples collected will then be de-identified and sent to Cancer Genetics Incorporated (CGI) for CYP3A5 genotyping. Results of the genotyping test will be incorporated into electronic medical record (EMR) in addition to the genotype-guided dosing recommendation for each patient. The initial tacrolimus dose will be based on genotype: 0.1 mg/kg/day (non-expressers) or 0.2 mg/kg/day (expressers) given in 2 divided doses; maximum total daily dose of tacrolimus is 20 mg/day. Eligible patients who consented to receive genotype-guided tacrolimus dose will enter the pharmacogenomic group and will receive the initial tacrolimus dosing based on genotype results following kidney transplantation (Study Day 1). Subsequent tacrolimus dosing will then be adjusted according to trough concentrations (C_0) and therapeutic target concentrations of 8-10 ng/mL (0 to 4 months), 6-8 ng/mL (5 to 12 months), and 5-7 ng/mL (>12 months). Dose adjustments and therapeutic drug monitoring will be conducted according to standard UNC-CH procedure. Hence, the genotype-guided dosing recommendation for tacrolimus only refers to the initial tacrolimus dose. All patients in the pharmacogenomic group will be followed from Study Day 2 and up to 12 months from the initiation of the first tacrolimus dose to assess long-term outcome (Follow-up Period). Safety and efficacy measures will be evaluated throughout the study per UNC-CH kidney transplant procedure.
 
Age-, race-, and disease-matched patients who had previously received kidney transplantation with standard tacrolimus dosing from 2010 to present will also be asked to give consent for genotyping (historical controls). These patients will be included in the control group and their safety and efficacy data will be collected retrospectively for up to 12 months from the initiation of first tacrolimus dose.

Study Duration	12-month follow up post-transplant
Study Center(s)	Single-center study
Objectives	Investigate the direct correlation of CYP3A5 genotype with tacrolimus trough levels and clinical outcomes. The primary endpoint of this study is to evaluate the proportion of patients reaching target levels (8-10 ng/ml) on Day 3 and Day 7 after kidney transplantation.

Number of Subjects	260
Inclusion/Exclusion Criteria	
Inclusion Criteria: All new kidney transplant recipients aged 18 to 65 years who are admitted at UNC-CH and provided informed consent will be included in this study (unless they meet exclusion criteria).
 
Patients will be excluded from participating in the study to receive genotype-guided tacrolimus dosing if he/she meets any of the exclusion criteria described below.
 
 • Recipients who did not consent to participate in the study. • Highly sensitized patients (ie, pretransplant T or B cell flow crossmatch positive) • Recipients of ABO incompatible kidney transplant • Recipients with preformed donor-specific antibodies (DSA) • HLA identical kidney transplant • Recipients of non-kidney transplant • Recipients of repeat transplant if they are on immunosuppression at the time of transplant • Patients using medications that have known pharmacokinetic (PK) drug interaction with tacrolimus • Patients in whom tacrolimus therapy is contraindicated
Study Product, Dose, Route, Regimen	All patients who consented will undergo genotype testing prior to transplant. Therapy for oral tacrolimus will be prescribed by the kidney transplant team as part of a standard immunosuppression agent given to kidney transplant recipients starting at 0.1 mg/kg/day (nonexpressers) or 0.2 mg/kg/day (expressers) given in 2 divided doses. The genotype-guided dosing only refers to the initial tacrolimus dose. Subsequent tacrolimus dosing will then be adjusted according to trough concentrations and desired therapeutic concentrations.
Reference therapy	
Pharmacogenomic group is compared to age-, race-, and disease-matched patients who received standard dose of tacrolimus as part of their immunosuppression regimen from 2010 to present (historical controls).
 
As the arrival of the donor kidney may come quickly and unexpectedly, it is possible that enrolled subjects may receive kidney transplantation prior to the incorporation of the CYP3A5 genotype result into EMR. In this case, patients will receive tacrolimus based on current standard tacrolimus dosing (0.1 mg/kg/day given in two divided doses) and will be included in the control group (prospective controls).
 
Hence, the control group will consist of both historical controls and potentially few prospective controls, if the scenario described above occurred.

Statistical Methodology	
All analyses will be performed on the basis of the ITT principle. Continuous variables will be summarized as medians with first to third quartiles. Appropriate conventional statistical analyses will be used to assess the primary and secondary endpoints. Categorical data will be compared using χ^2 or Fisher's exact test, as appropriate; some comparisons will require correction for potential confounders such as race/ethnicity; these will be performed using the Cochrane-Mantel-Haenszel test. Continuous variables will be compared using the Wilcoxon test or the t-test. The incidence of an adverse outcome (ie, graft rejection, graft loss, renal impairment, tacrolimus toxicities, and death) will be estimated using Kaplan-Meier curves. Depending on the distribution of the data, time-to-event (ie, time to reach therapeutic target range) analysis will be performed using an appropriate parametric, nonparametric, or semi-parametric survival analysis method.

--------------------------------	--

1 Ethical Considerations

This is a clinical study protocol for a human research study. This study is to be conducted according to United States (US) and international standards of Good Clinical Practice (FDA Title 21 part 312 and International Conference on Harmonization [ICH] guidelines), applicable government regulations, and Institutional research policies and procedures grounded on the principles found within the Declaration of Helsinki.

This protocol and any amendments will be submitted to a properly constituted Independent Ethics Committee (IEC) or Institutional Review Board (IRB), in agreement with local legal prescriptions, for formal approval of the study conduct. The decision of the IEC/IRB concerning the conduct of the study will be made in writing to the investigator and a copy of this decision will be provided to the sponsor before commencement of this study. The investigator should provide a list of IEC/IRB members and their affiliate to the sponsor.

It is expected that the IRB will have the proper representation and function in accordance with federally mandated regulations. The protocol, Investigator's Brochure, informed consent, advertisements (if applicable), written information given to the patients, safety updates, annual progress reports , and any revisions to these documents will be provided to the IRB/IEC by the investigator.

1.1 **Subject Information and Consent**

All subjects for this study will be provided a consent form describing this study and providing sufficient information for subjects to make an informed decision about their participation in this study. See Attachments 1, 2, and 3 for copies of the Subject Informed Consent Form. This consent form will be submitted with the protocol for review and approval by the IEC/IRB for the study. The formal consent of a subject, using the IEC/IRB-approved consent form, must be obtained before that subject undergoes any study procedure. The consent form must be signed by the subject or legally acceptable surrogate, and the investigator-designated research professional obtaining the consent.

A written informed consent form, which contained all US federally required elements, all ICH-required elements, and Health Insurance Portability and Accountability Act (HIPAA) Authorization information in language that was understandable to the subject, will be given to each subject. The process of obtaining the informed consent will be in adherence with all federal regulations, ICH requirements, and local laws.

In obtaining and documenting informed consent, the investigator should comply with the applicable regulatory requirement(s), and should adhere to Good Clinical Practice (GCP) and to ethical principles that have their origin in the Declaration of Helsinki.

Before recruitment and enrollment onto this study, the patient will be given a full explanation of the study and will be given the opportunity to review the consent form. Each consent form must include all the relevant elements currently required by the FDA Regulations and local or state regulations. Once this essential information has been provided to the patient and the investigator is assured that the patient understands the implications of participating in the study, the patient will be asked to give consent to participate in the study by signing an IRB-approved consent form prior to study participation.

Prior to a patient's participation in the trial, the written informed consent form should be signed and personally dated by the patient or the patient's legally acceptable representative, and by the person who conducted the informed consent discussion.

2 Introduction

This is a single-center study of pharmacogenomic-guided tacrolimus dosing and monitoring in kidney transplant recipients.

2.1 Background and Rationale

Renal transplantation from either a live or deceased donor has become the preferred treatment for patients with end-stage renal disease because it prolongs survival and improves quality of life (Port 1994; Schnuelle et al. 1998; Tonelli et al. 2011). Tacrolimus is the standard treatment for immunosuppression with kidney transplant patients as tacrolimus is associated with better graft survival and lower incidence of nephrotoxicity compared to cyclosporine (Bowman and Brennan 2008; Webster et al. 2005a; Webster et al. 2005b).

Tacrolimus is a good candidate for pharmacogenomic-guided dosing and monitoring as it displays variable pharmacokinetics and is also a narrow therapeutic index drug, whereby low drug exposure increases risk to kidney rejection and high doses correlate with nephrotoxicity (Birdwell et al. 2015; Hesselink et al. 2014; Provenzani et al. 2013). Reaching and maintaining therapeutic tacrolimus levels is also often problematic despite adjustment of the initial dose to body weight and frequent monitoring of tacrolimus levels. Furthermore, response to tacrolimus is dose-dependent with large intra- and inter-patient variability that has been partly attributed to genetic differences in the *CYP3A5* gene (Birdwell et al. 2015; Hesselink et al. 2014; Provenzani et al. 2013; Staatz, Goodman, and Tett 2010a, b).

The *CYP3A5* gene encodes for the drug-metabolizing enzyme CYP3A5, which is primarily responsible for the hepatic and renal clearance of tacrolimus (Dai et al. 2006). Specifically, the single nucleotide polymorphism (SNP), rs776746, results in a functional variation that substitutes an adenine (A) for a guanine (G) at position 6986 within intron 3 of the *CYP3A5*. A change from A to G at this position creates a cryptic splice site in intron 3 that results in an alternatively spliced isoform that has an insertion in intron 3. This alternative spliced mRNA alters the reading frame and results in a premature termination codon that leads to a nonfunctional protein (Birdwell et al. 2015; Lamba et al. 2012; Staatz, Goodman, and Tett 2010a, b). The nonfunctional CYP3A5 enzyme corresponds to the *CYP3A5*3* allele, while the functional allele is considered *CYP3A5*1*. Patients who have one (*CYP3A5*1/*3*) or both copies of the functional allele (*CYP3A5*1/*1*) are considered *CYP3A5* expressers. Due to high *CYP3A5* expression, patients with *CYP3A5*1/*1* or *CYP3A5*1/*3* genotype may have lower levels of tacrolimus than patients with *CYP3A5*3/*3* genotype, predisposing them to reduced immunosuppressive effects that may lead to acute kidney rejection. On the other hand, patients who have *CYP3A5*3/*3* genotype do not express *CYP3A5* (*CYP3A5* nonexpressers), which can lead to increased risk for toxicities due to supratherapeutic tacrolimus levels (Birdwell et al. 2015; Lamba et al. 2012; Staatz, Goodman, and Tett 2010a, b; van Gelder, van Schaik, and Hesselink 2014). In line with these findings, the Clinical Pharmacogenetics Implementation Consortium (CPIC) has recently published guidelines for *CYP3A5* genotyping and tacrolimus dosing (Birdwell et al. 2015).

The *CYP3A5* 6986A>G (rs776746) variant is ideal for a pharmacogenomic study as it has a high estimated allele frequency across various populations, including Whites (82% to 95%), Japanese (85%), Southeast Asians excluding Japanese and Chinese (67%), Chinese (65%), Pacific Islanders (65%), Southwest American Indians (40%), and African Americans (33%) (Lamba et al. 2012). The *CYP3A5* 6986A>G genotype has been consistently associated with tacrolimus clearance and trough levels (Macphee et al. 2005; Macphee et al. 2002; Quteineh et al. 2008; Renders et al. 2007; Thervet et al. 2003; Zhang et al. 2005; Zheng et al. 2003). In a recently published review and meta-analysis, the functional *CYP3A5*1* allele was associated with higher risk of acute rejection and chronic nephrotoxicity (Rojas et al. 2015).

Whether pharmacogenomic-guided dosing leads to improved clinical outcomes is yet to be determined. A prospective study conducted in France showed that genotype-guided dosing resulted in quicker time to reach therapeutic tacrolimus levels but did not demonstrate improved clinical outcomes compared to standard dosing (Thervet et al. 2010). Furthermore, a recent study in Netherlands did not find any difference in the incidence of acute rejection or in the proportion of patients with sub or supratherapeutic tacrolimus levels when comparing subjects who received genotype-guided vs. standard tacrolimus dose (Shuker et al. 2016). Of note, a difference in tacrolimus trough levels and dose requirement was observed between *CYP3A5* expressers and nonexpressers throughout the 3-month period (Shuker et al. 2016). In

both these studies, the population was primarily low-risk (living donor recipients) and was mostly Caucasian (90%).

To further investigate if these results are relevant in the US kidney transplant population, particularly in centers comprising of at least 40% African Americans who are likely to carry the *CYP3A5*1* (expressers) allele and be under-dosed, we are proposing a prospective, single-center study in the US that is aimed at evaluating the relationship between genotype-guided tacrolimus dosing, drug concentrations, and clinical outcomes. Unlike the study population in both European studies, the transplant recipients here at the University of North Carolina in Chapel Hill (UNC-CH) comprise of at least 40% African Americans, with majority of the kidney transplant recipients (75%) receiving their kidneys from deceased donors and are therefore more likely to be at risk for poorer outcomes. Unlike the standard tacrolimus dosing and target tacrolimus levels used by Thervet and colleagues in France, the tacrolimus dosing algorithm and therapeutic target levels being used at UNC-CH is more representative of the regimen for tacrolimus in the US kidney transplant recipients. Additionally, unlike the immunosuppressant regimen used by Thervet *et al* and Shuker *et al*, the immunosuppressant regimen that are currently being used at UNC-CH are representative of the current therapeutic management of US kidney transplant recipients. The standard tacrolimus dosing algorithm currently being used at UNC-CH was developed in accordance to current clinical guidelines and will be considered in the study as standard therapy. To provide a comparable pharmacogenomic-guided algorithm, the genotype-guided dosing algorithm described in [Section 6.2.1](#) is similar to the one that was used in France (Thervet *et al.* 2010) and Netherlands (Shuker *et al.* 2016). Hence, the results of this study will provide more relevant findings for the US kidney transplant population as well as provide a reasonable comparison from previous and recently published pharmacogenomic studies in Europe.

In addition, the results of this study will allow us to explore the feasibility of using genotype information for clinical decision making as well as the economic impact of using a genotype-guided treatment algorithm at UNC-CH kidney transplant unit.

2.2 Previous Clinical Experience with Genotype-Guided Tacrolimus Dosing

There are two large prospective pharmacogenomic studies that have tested the efficacy and safety of two genotype-guided tacrolimus doses: 0.15 mg/kg/day for *CYP3A5* expressers and 0.3 mg/kg/day for *CYP3A5* nonexpressers (Shuker *et al.* 2016). In both studies, there was no difference in safety outcomes between subjects who received standard tacrolimus dosing (0.2 mg/kg/day) versus those who received genotype-guided dosing (0.15 or 0.3 mg/kg/day). There were no significant between-group differences in the overall incidence and severity of biopsy-proven acute rejection (BPAR), rate of acute and delayed graft rejection, and incidence of adverse events, including infection, tacrolimus-associated nephrotoxicity, and post-transplant diabetes mellitus.

Additionally, the genotype-guided dosing recommendation used in previous studies (Shuker *et al.* 2016), which is similar to the one proposed in this study protocol, follows the recommendation outlined in the Clinical Pharmacogenetics Implementation Consortium (CPIC) guideline (<https://www.pharmgkb.org/guideline/PA166124619>). CPIC's genotype-guided dosing recommendation for tacrolimus was classified as "strong" based on a combination of preclinical functional and clinical data as well as on some existing disease-specific consensus guidelines.

Taken together, in addition to fact that genotype-guided dosing will only be given ONCE at the initial dosing of tacrolimus (subsequent dosing will then be based on tacrolimus trough levels and desired therapeutic concentration in accordance to standard procedure), the investigators do not anticipate any additional risks for subjects who will receive genotype-guided therapy compared to the standard tacrolimus dose that would have been given as part of their immunosuppressant regimen in the event that subjects do not consent to be included in the study.

3 Study Objectives

The primary objective of this study is to investigate the direct correlation of *CYP3A5* genotype with tacrolimus trough levels and clinical outcomes. To meet this objective, a comparison of the primary and

secondary endpoints will be conducted between kidney transplant recipients who underwent prospective pharmacogenomic-guided tacrolimus dosing strategy (pharmacogenomic group) and patients who received standard tacrolimus dosing regimen historically and prospectively (control group). Patient data from the control group will be obtained from 2010 until the end of study period.

The secondary objective of this study is to assess the economic benefit of genotype-guided tacrolimus dosing as measured by direct healthcare cost.

Additionally, we will store banked DNA for future unspecified research from individuals who agree to participate in this study that are undergoing kidney transplantation at UNC-CH. A pharmacogenomic database will be created and maintained in a secure database for possible use in future studies to retrospectively correlate pharmacogenomics (SNPs and patterns of polymorphisms) with therapeutic drug monitoring levels and clinical metrics (eg., Quality/ Safety Metrics – mortality, morbidity, and other quality markers (eg., length of hospital stay, readmission rate etc). We plan to use genomic samples to base clinical care on genetic variants with known functional impact (ie, CYP2D6, TMPT, G6PD etc.). We therefore propose to study other smaller effect loci identified by association studies using the data for hypothesis generating analysis to correlate these single gene polymorphisms and polymorphism patterns with clinical outcomes by creating and then using a pharmacogenomic database.

3.1 Primary Endpoint

The primary endpoint of this study is to evaluate the proportion of patients reaching target levels (8-10 ng/ml) on Day 3 and Day 7 after kidney transplantation.

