As the arrival of the donor kidney may come quickly and unexpectedly, it is possible that enrolled subjects may receive kidney transplantation prior to the incorporation of the *CYP3A5* genotype result into EMR. In this case, patients will receive tacrolimus based on current standard tacrolimus dosing (0.1 mg/kg/day given in two divided doses) and will be included in the control group (prospective controls). Throughout the study, safety and efficacy measures will be evaluated in the prospective controls per UNC-CH kidney transplant procedure. These patients will also be followed from Study Day 2 and up to 12 months from the initiation of the first tacrolimus dose to assess long-term outcome (Follow-up Period).

Additionally, age-, race-, and disease-matched patients who had previously received kidney transplantation with standard tacrolimus dosing will also be asked to give consent for genotyping (historical controls). These patients will also be included in the control group and their safety and efficacy data will be collected retrospectively for up to 12 months from the initiation of first tacrolimus dose. Hence, the control group will consist of both historical controls and potentially few prospective controls, if the scenario described above occurred.

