6.2 Treatment Regimen

All patients who consented will undergo genotype testing prior to transplant. The genotype-guided dosing recommendation as shown in **Figure 3** below only refers to the initial tacrolimus dose. Subsequent tacrolimus dosing will then be adjusted according to trough concentrations and desired therapeutic concentrations. Therapy for oral tacrolimus will be prescribed by the kidney transplant team as part of a standard immunosuppression agent given to kidney transplant recipients starting at 0.1 mg/kg/day (nonexpressers) or 0.2 mg/kg/day (expressers) given in 2 divided doses; maximum total daily dose of tacrolimus is 20 mg/day.

As the drug and the doses being used are not investigational, tacrolimus will be stored and dispensed in accordance to current UNC-CH pharmacy procedures. The patients and investigators will not be blinded in the study, hence there will be no procedure related to blinding of study drug.

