8.2 Sample Size Determination

The primary endpoint of this study is to evaluate the proportion of patients reaching target levels (8-10 ng/ml) on day 3 and day 7 after kidney transplantation.

We calculated that a total study population of 260 patients (pharmacogenomics group = 130; control group = 130 patients) would be sufficient to provide a statistical power of 90% to detect a significant difference between the two groups, on the basis of a two-sided χ^2 test, a significance level of 5%, a frequency of approximately 50% for the *CYP3A5*3/*3* genotype, and a 40% and 60% frequency of the primary endpoint in the control and pharmacogenomic group (Thervet et al. 2010), respectively. Because of the nature of the study design we anticipate a small rate of sample dropout (<5%), which should not appreciably impact the power of the study.

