Statistical testing, whenever performed, will be 2-sided with a significance (alpha) level of 0.05. In addition, 95% confidence intervals will also be determined. All statistical analyses will be conducted using SAS® or other appropriate statistical programs.

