10.4.3 Missing Data

The main problem from missing data will be missing tacrolimus blood levels either from attrition or missed visits. Given that the initial monitoring of tacrolimus (Day 3 and Day 7) for the primary outcome will be conducted at the hospital, we expect the issue of attrition and missing data to be very unlikely. Extensive efforts will be made to collect complete information on each subject enrolled throughout the study. The optimal approach to missing data is to be proactive and be diligent in avoiding it. Additional methods, including calendar alerts, e-mail reminders, and reminder calls may be employed to minimize missed visits.

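### The primary endpoint names Day 3 and Day 7 but gives no rule for combining them, so the stated 5% error and 90% power hold under only some readings

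*Combined protocol and SAP*

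**What the plan says.** The Study Summary (Objectives), Section 3.1 and Section 8.2 give the primary endpoint in near-identical words: "the proportion of patients reaching target levels (8-10 ng/ml) on Day 3 and Day 7 after kidney transplantation". Section 10.4.3 names the same two days: "Given that the initial monitoring of tacrolimus (Day 3 and Day 7) for the primary outcome will be conducted at the hospital". None of these says whether a patient must be in range on both days or on at least one, or whether each day is a comparison of its own.

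Section 8.2 specifies a two-sided chi-square test at 5% with 130 patients per group. It assumes "a 40% and 60% frequency of the primary endpoint in the control and pharmacogenomic group", citing an earlier prospective study, and concludes that this "would be sufficient to provide a statistical power of 90% to detect a significant difference between the two groups". No day or composite is attached to the rates.

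Section 8.3 ties no particular test to the primary endpoint. Its rule on error is general: "Statistical testing, whenever performed, will be 2-sided with a significance (alpha) level of 0.05". It contains no multiplicity rule.

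Two features of the design bear on this. Section 6.2 states that "The patients and investigators will not be blinded in the study". For the historical controls, Section 4.3 says that "their safety and efficacy data will be collected retrospectively for up to 12 months from the initiation of first tacrolimus dose".

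**The concern.** This is the trial's main decision rule, and the text admits at least four outcomes: Day 3 alone, Day 7 alone, both days, and at least one day. It also admits two ways of declaring success if the days are tested separately. These differ in error rate, in power and in what a positive result means.

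The gap matters more here than in a blinded randomised trial. Treatment is open, and the historical controls' trough levels are already in their records. Section 8.4 keeps outcome data and genotype from the statistician who selects the controls. That protects the matching but does not fix the endpoint. As written, the definition could be settled after levels are known.

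**Working it through.** **Inputs from the documents.** 130 per group, two-sided alpha 0.05, chi-square test, rates 40% and 60% (Section 8.2); 0.05 for each test (Section 8.3).

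**Inputs assumed.** The documents give no correlation between Day 3 and Day 7, so 0 to 0.9 is used. Where the days are treated separately, 40%/60% is assumed on each day.

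**1. The plan's own figure.** With pooled variance under the null and no continuity correction, n per group = [1.96 × √(2 × 0.5 × 0.5) + 1.2816 × √(0.4 × 0.6 + 0.6 × 0.4)]² / 0.20² = 129.3, rounded up to 130, or 260 in total. Power at 130 is Φ[(0.20 − 1.96 × √(0.50/130)) / √(0.48/130)] = Φ(1.291) = 90.2%. The plan's figure is reproduced for one binary outcome tested once.

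**2. Each day tested at 0.05, success on either.** Familywise error = 1 − P(|Z₁| ≤ 1.96 and |Z₂| ≤ 1.96), with Z₁, Z₂ bivariate normal. At correlation 0 this is 1 − 0.95² = 9.75%.

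**3. Each day tested at 0.05, both must be significant.** Power = P(both standard normals ≤ 1.291). At correlation 0 this is 0.9017² = 81.3%.

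| Correlation of the two tests | Error, either day succeeds | Power, both must succeed |
|---|---|---|
| 0 | 9.75% | 81.3% |
| 0.3 | 9.5% | 82.4% |
| 0.5 | 9.1% | 83.5% |
| 0.7 | 8.4% | 84.9% |
| 0.9 | 7.0% | 87.1% |

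**4. One per-patient composite, with 40%/60% as per-day rates.** If p is the per-day rate and φ the within-patient correlation, the chance of being in range on both days is p² + φp(1 − p). That is 0.16 + 0.24φ in controls and 0.36 + 0.24φ in the pharmacogenomic group. The group difference is therefore 0.20 + 0.24 × (φ pharmacogenomic − φ control).

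- Equal φ: the difference stays at 20 points. Rates are 16%/36% (φ = 0), 28%/48% (0.5) and 37.6%/57.6% (0.9), with power 96.1%, 91.8% and 90.2%.
- Unequal φ, for example 0.5 in controls and 0.3 in the pharmacogenomic group: 28.0% against 43.2%, a difference of 15.2 points. Power = Φ[(0.152 − 1.96 × 0.0594) / 0.0586] = 72.8%.
- For at least one day, the chance is 2p minus the chance of both, and the sign of the φ term reverses. With φ of 0.3 in controls and 0.5 in the pharmacogenomic group the rates are 56.8% and 72.0%, and power is again 72.8%.

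**5. Definition chosen after the data.** In simulation under no difference (rate 40% on each day in both groups), taking the best of Day 3, Day 7, both days and at least one day rejects in about 15.3% of trials at φ = 0, 12.7% at 0.5 and 8.2% at 0.9.

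**The case against.** The strongest reply is that the natural reading leaves the plan intact. The documents speak of one endpoint and one outcome, join the days with a conjunction, and size the trial with one test, one alpha and one pair of rates. Under that reading alpha is 5%, and power is 90.2% if 40% and 60% are the composite's own rates. No section announces two separate tests or a choice made after the data. All of this stands as far as it goes: the wording leans towards a single per-patient outcome. It is still not a definition. Even then, both days and at least one day remain open, and with 40%/60% per day and no correlation they are outcomes of 16%/36% and 64%/84%.

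Four stronger readings are tempting, and the documents do not support them.

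- A reader might infer that 260 patients is a miscalculation or that the trial is underpowered. It reproduces exactly for one outcome at 40% against 60%.
- A reader might infer that testing the days separately must break the 5% level. It does not: a fixed sequence tests them separately and keeps 5%. The loss comes from separate tests without an ordering, or from requiring both.
- A reader might infer the opposite comfort, that any composite has at least 90% power if each day's rates are 40%/60%. That needs equal within-patient correlation in the two groups. No section supports this, and only the initial dose differs by design before trough-guided adjustment takes over.
- A reader might infer that the 40%/60% rates are mismatched to the endpoint. The plan does not say what they describe in the cited study, so a mismatch can be neither shown nor excluded.

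**Conclusion.** The concern holds as a gap in the definition with calculable consequences. The stated 5% and 90% are right for a single pre-fixed outcome whose own rates are 40% and 60%. They are not right if the 0.05-per-test rule of Section 8.3 is applied to each day without an ordering: familywise error is then 7.0% to 9.75%, or power about 81% to 87%, depending on the success rule. For a composite built from per-day rates, power is 90% to 96% with equal within-patient correlations, but can be about 73% with unequal ones. A choice made after the data would carry an error of about 8% to 15%.

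The correlations and the per-day use of 40%/60% are assumptions; the reproduction of 260 is not. The harm depends on which reading is applied, so this should be corrected but does not invalidate the design.

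**What to change.** Before outcome data are examined, state one rule in identical words in the Study Summary and Sections 3.1, 8.2 and 8.3. Either:

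- (a) one per-patient responder, in range on both Day 3 and Day 7 (the literal meaning of the present wording), tested once at two-sided 0.05, with each single day reported descriptively; or
- (b) a fixed sequence, Day 3 at two-sided 0.05, then Day 7 at 0.05 only if Day 3 is significant.

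State which outcome the 40% and 60% describe. If they are not the rates of the tested outcome, restate the power with the assumed correlation in each group. Under (b), the 90% applies to Day 3 only if these are the Day 3 rates; the chance of claiming both days is the 81% to 87% above.

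The cost is wording. No new data are needed, and no change in sample size if 40%/60% are the rates of the tested outcome. Under (a), single-day results are not confirmatory. Under (b), an effect seen only on Day 7 cannot be claimed. The alpha for the interim analysis in Section 9.5 is a separate matter.
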